**IX. Payment or Token of Appreciation:**

- A. *Do you plan to provide a non-monetary token of appreciation (food, soap, tea, chlorine tablets, etc.) to study participants? If no payment is provided, the JHSPH IRB strongly encourages providing such tokens. If yes, please describe below.*

[DPP Cooks participants will receive a Participant Workbook (attached) that will accompany and serve as a resource for the cooking classes. They will also receive food for the recipes that will be cooked at each class and will be able to take any left over food home with them. In the standard DPP arm, participants will also be offered the Participant Workbook and a cooking class (with accompanying food) at the conclusion of the 12 months. Participants who opt in will also be provided a CGM for 14 days at baseline and 12 months.]

]

- B. *If you plan to provide a monetary payment, describe the form, amount, and schedule of payment to participants. Reimbursement for travel or other expenses is not “payment,” and if the study will reimburse, explain.*

[ All participants will be compensated \$100 (\$20 after baseline data is completed, \$20 after 4 month data collection is completed, and \$60 after 12 month data collection is completed). ]

- C. *Include the possible total remuneration and any consequences for not completing all phases of the research.*

[ If participants do not complete all phases of the study they will only be compensated for the phases they did complete. ]

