**III. Study Design:**

A. *Provide a BRIEF overview of your study design and methods. The study design must relate to your stated aims/objectives. DETAILS WILL BE REQUESTED LATER. If your study also involves analysis of existing data, please complete Section XI, "Secondary Data Analysis of Existing Data" in the last part of this research plan. If your study ONLY involves analysis of existing data, please use the research plan template for secondary data analysis (JHSPH IRB Research Plan for Secondary Data Analysis of Existing Data/Specimens).*

This study is a randomized control pilot trial testing the DPP Cooks against standard DPP. DPP is a 12 month diabetes prevention behavioral weight loss program developed by the CDC and implemented

nation wide. Participants meet weekly for the first 6 month in group sessions, then meet less frequently over the last 6 months to help them maintain the behavioral changes (re: diet and physical activity) they made in the first six months. For this trial, up to 48 participants will be randomized 1:1 to participate in the 12 month DPP or the 12 month DPP *plus* an additional 6 cooking skills sessions (DPP Cooks) during the first 4 months of the DPP. The primary outcome, weightloss, is collected at weekly DPP sessions. The secondary outcomes will be collected via online surveys at baseline, 4 months and 12 months, and via the Remote Food Photography Method (RFPM) at baseline and 4 months.

- B. *Provide a sample size and a justification as to how you arrived at that number. If you use screening procedures to arrive at a final sample, distinguish the screening sample size from the enrolled sample size; a table may be helpful. For electronic survey studies involving online recruitment and survey completion: consider how you will set controls on how many people will join your study.*

The target sample size of 48 individuals, randomized 1:1 was based on the fact that this is a pilot feasibility trial so we are not necessarily concerned with detecting statistically significant results. Budget constraints preclude a higher sample size. This sample size will allow us to test the DPP Cooks with several cohorts to understand implementation and prepare for a larger, fully powered study in the future.

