The standard DPP group (control) will be offered a cooking skills session at the completion of the study as well as a participant workbook from the DPP Cooks.

All participants will have the following data collected:

Measure	Method	Baseline	4 months	12 months
Weight loss (kg and % of body weight)	In DPP meetings	X	X	X
Diet quality (3 days at each timepoint)	RFPM	X	X	
Cooking skills/ attitudes/ behaviors	Online Survey	X	X	X
Food Agency	Online Survey	X	X	X
Cooking confidence	Online Survey	X	X	X
Food security status	Online Survey	X	X	X
Demographics	Online Survey	X		
Acceptability of the DPP cooks	Interview			X
DPP session attendance	DPP Coaches			X

- ]
2. *Describe the number and type of study visits and/or contacts between the study team and the participant, how long they will last, and where/how they will take place.*

[ As described above, participants will participate in the DPP, which meets weekly for approximately 1 hour for six months, then approximately monthly for the last 6 months. Participants in the intervention arm (DPP Cooks) will have an additional 6 sessions in a teaching kitchen (2 hours each, 12 hours extra total). If the teaching kitchen is not open due to COVID-19 transmission rates, cooking classes will be held virtually over Zoom. If cooking sessions are virtual, study team staff will deliver the food and equipment needed to participant's homes. Study staff will maintain a safe distance when they deliver and will not enter participant's homes. Staff will drop off food and make sure it is received.

**We begin this study with virtual DPP Cooks classes. We will not begin in person classes at the teaching kitchen until we have been approved by the IRB to do so.**

The DPP Cooks arm will also be sent text messages during the latter 8 months of the intervention (after the 6 cooking sessions are complete) to act as cues to action to keep cooking and using the skills and recipes they developed.

Weight loss data will be collected per usual during DPP sessions by the coach. During virtual DPP, weight has been self-reported by the participant using DPP provided scales. Weight data is reviewed by the DPP team for quality and any issues are resolved with the participant. Weight data is collected in compliance with CMS standards. Weight data will be inputted by DPP staff into a spreadsheet saved on OneDrive. Participants will be identified by their study ID number only.

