Diet quality will be collected by the participant by taking photographs of all the food they eat over a 3-day period and uploading those photographs to the SmartIntake app. Participants will be reminded to do this based on text messages from the study team, and the study team will be on hand to assist participants if they run into any problems or need help. Participants will be given a reference card to include in food photographs (e.g. a blank white card with some lines on it to help gauge portion size as well as a paper food tracker and guidebook). Other measures of interest will be collected using online surveys (Qualtrics) at baseline, 4 months and 12 months. Finally, we will invite participants to share their thoughts and experiences with the DPP Cooks intervention in in-depth interviews (over Zoom or phone) at the end of the study (12 months).

]

- [ ]
3. *Describe the expected duration of the study from the perspective of the individual participant and duration overall.*

[The duration of the study is 12 months from start to finish. From the participant's perspective they will attend DPP sessions and some participants will have 6 extra cooking classes. Data collection will not require in person study visits. The participant will have a training session with study team staff to help them install and learn how to use the RFPM app and record their data. This session will take place over zoom before baseline data collection begins.

]

4. *Provide a brief data analysis plan and a description of variables to be derived.*

[The key independent variable for all analyses is an indicator of whether or not the participant is in the control (standard DPP) group or the intervention (DPP Cooks) group. The other key variable is an indicator of time (baseline, 4 months, or 12 months). The primary outcome variables are weight loss (in kg lost, and in % of body weight lost). The secondary outcome variable is dietary intake/quality. We will use the data from the RFPM to calculate Healthy Eating Index-2015 scores. We will also be able to measure fruit and vegetable, as well as carbohydrate intake. Additional secondary outcomes from survey measures will include cooking confidence, cooking attitudes, cooking behaviors, cooking skills, food agency, and food security status. For most analyses we will compare changes in scores from baseline to 4 months and baseline to 12 months between intervention and control groups.]

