5. **Answer the following if they are relevant to your study design:**

- A. *If the study has different arms, explain the process for assigning participants (intervention/control, case/control), including the sequence and timing of the assignment.*

[DPP cohorts will be the unit of randomization to avoid cross over due to the group meeting format of the DPP. Randomization will occur the same way for everyone regardless of how they are recruited. We will run 2 DPP cohorts concurrently and one will be the intervention arm, and one will be the control arm. Participants will be assigned to the two study arms randomly. Once participants enroll in the study, they will be assigned to the 2 study arms using a random number function in Excel. Because the intervention requires a weekly DPP meeting, and this needs to fit in to the participant's life, we will create cohorts for randomization for whom 2 DPP meetings would be convenient. For example, if there is a DPP group on Thursday at 5:00 and another on Wednesday at 6:00 or 2 Thursday at 5:00 groups, we will create a spreadsheet of individuals for whom DPP meetings on Thursday at 5:00 or Wednesday at 6:00 will work. Then, we will use the random number function in Excel to assign those participants to 2 groups. We will also randomly determine which DPP cohort will be the intervention and which will be the control.]

- B. *If human biospecimens (blood, urine, saliva, etc.) will be collected, provide details about who will collect the specimen, the volume (ml) and frequency of collection, how the specimen will be used, stored, identified, and disposed of when the study is over. If specimens will be collected for use in future research (beyond this study), complete the "Biospecimen Repository" section below.*

[n/a ]

- C. *If genetic/genomic analyses are planned, address whether the data will be contributed to a GWAS or other large dataset. Address returning unanticipated incidental genetic findings to study participants.*

[n/a ]

D. If clinical or laboratory work will be performed at JHU/JHH, provide the JH Biosafety Registration Number.

[n/a ]

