- C. *Describe the anticipated frequency and severity of the harms associated with the risks identified above; for example, if you are performing "x" test/assessment, or dispensing "y" drug, how often do you expect an "anticipated" adverse reaction to occur in a study participant, and how severe do you expect that reaction to be?*

[ We do not anticipate any of the risks involved would be greater than those expected during daily life. ]

- D. *Describe the research burden for participants, including time, inconvenience, invasion of privacy in the home, out of pocket costs, etc.*

[ Participants will participate in the DPP (at least 16 weekly sessions of the first 6 months and at least 6 sessions in the last 6 months) and in the DPP Cooks arm will also participate in 6 2-hour cooking classes over the first 4 months. Participants will answer surveys at 3 time point, will complete 3 days of dietary recall (by taking pictures on their smart phone) at 2 time points, and will have the option to wear a CGM for 14 days at 2 time points. They will also have the option to participate in an in-depth interview after the completion of the program. In total, data collection activities should be a minor inconvenience and time commitment. Invasion of privacy is a very low risk and we do not anticipate any out of pocket costs. ]

- E. *Describe how participant privacy, and if relevant – family privacy - will be protected during data collection if sensitive questions are included in interviews, or if study visits occur in the home setting.*

[ Sensitive questions are not included in any data collection documents and there are no in person or in home data collection activities. ]

]

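### Does the opt-in CGM, offered in two places but absent from the measures table and analysis plan, call for a change to the plan?

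*Combined protocol and SAP*

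**What the plan says.** The CGM is mentioned twice. Section VII.D, on research burden, says participants "will have the option to wear a CGM for 14 days at 2 time points", without naming the time points. Section IX.A, under tokens of appreciation, names them: "Participants who opt in will also be provided a CGM for 14 days at baseline and 12 months".

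The outcomes are set out elsewhere. Section I makes weight loss primary and lists diet, cooking measures and class attendance as secondary. Section V.C.4 defines weight loss in kg and as a percentage of body weight, takes dietary variables from the food photographs, and then says "Additional secondary outcomes from survey measures will include cooking confidence, cooking attitudes, cooking behaviors, cooking skills, food agency, and food security status". The table in V.C.1 schedules the measures. The only participant training described, in V.C.3, concerns food photography: "The participant will have a training session with study team staff to help them install and learn how to use the RFPM app". The risks in VII.A are cuts or burns, food allergy and loss of confidentiality.

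On the population, section I says the comparison is among low-income adults. Sections IV.A and IV.B and the telephone screening steps in V.B contain no income item.

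**The concern.** A wearable sensor is offered to as many as 48 people, yet the plan gives it no supply route, training, named data destination, derived variable or device risk. VII.D lists it beside the surveys and food photographs, as if it were a measure; IX.A lists it as a token. Section II adds to the doubt by saying the findings will bear on diabetes indicators, although no glycaemic outcome is defined.

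If glucose data were collected and later reported, the analysis would be post hoc and the sample self-selected. Section V.C.5.A says "Once participants enroll in the study, they will be assigned to the 2 study arms using a random number function in Excel", but nothing says whether participants opt in before or after they learn their arm. A comparison between arms among device users could therefore be biased by selection.

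The income wording raises a related worry: conclusions might be stated for low-income adults from a sample that was never restricted by income.

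**Working it through.** No formula applies. The check sets the sections side by side.

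**1. Where the CGM appears.** VII.D and IX.A: 2 mentions. Design overview (III.A), procedures (V.C.1 to V.C.3), analysis plan (V.C.4) and risk list (VII.A): 0 mentions. Glucose otherwise appears only in the DPP eligibility criteria.

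**2. Measures table (V.C.1).** The rows are weight loss, diet quality, cooking skills/attitudes/behaviors, food agency, cooking confidence, food security, demographics, acceptability and session attendance. That is 9 rows, of which 0 are glycaemic.

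**3. Whether optional status explains the gap.** It does not. VII.D also makes the interview optional, "They will also have the option to participate in an in-depth interview after the completion of the program", and the interview has its own row, "Acceptability of the DPP cooks". The CGM was left out for some other reason.

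**4. What depends on the CGM.** V.C.4 names two weight variables, the dietary variables from the photographs and six survey outcomes. Section I adds class attendance. None is computed from CGM readings. The target of 48 in III.B is justified by pilot status and budget, with no formula into which a glucose measure could enter. Planned results affected: 0.

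**5. Arguments that seem to enlarge the gap.**
- *III.A restricts secondary outcomes to surveys and photographs.* It does not. Class attendance is secondary in section I and is recorded by DPP coaches, which is neither route. Absence from III.A therefore proves little.
- *The second wear has no diet measure beside it.* Photographs are taken at baseline and 4 months, and the second wear is at 12 months, a gap of 12 − 4 = 8 months. This matters only if the CGM was meant to be read against diet, which the documents never say. Weight and surveys are collected at 12 months.
- *A comparison among users is randomised only if opt-in precedes assignment.* This is too strict. Opt-in after assignment, but before the arm is known, would also preserve it. Opt-in before assignment would not protect against selective non-wear at 12 months. In any case, no such comparison is planned.
- *The device tables in XVI are blank.* Blank fields are weak evidence in this form. The survey-platform field in VI.7 is also blank, although V.C.2 names Qualtrics.

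**6. Income.** Income items: 0 of 3 numbered inclusion criteria, 0 of the DPP criteria and 0 of 4 exclusion criteria. Against that, V.A directs outreach to named public-housing sites near the venue, though it also includes a posting for students and faculty. V.C.1 schedules demographics at baseline and food security at all three time points. The demographic questions are not in the documents, so income may already be asked.

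**The case for a change.** The strongest case for a change is that this is the current text, and staff who follow it would hand out the device. Both readings leave work undone. A measure needs a row, a data flow and an analysis; a token still needs a description of supply and an entry under risks and devices. The repair is cheap, and settling the status of glucose data in advance is better than deciding after the data are seen.

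Much of this stands. The token-or-measure ambiguity is real, and so are the gaps in the procedures and in VII.A. They are matters of completing the form, however. The only section that gives the timing treats the device as a token, and a token needs no outcome row or estimator. If glucose readings were reported from a pilot of at most 48, a competent analyst would describe them, show uptake by arm and label them as coming from volunteers. The plan claims nothing stronger.

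On income, an aim may name the population a programme is meant to serve without an eligibility cut-off. The remaining mismatch could be closed equally well by rewording the aim or by adding a criterion, and no analysis turns on the choice.

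**Conclusion.** The omission is confirmed: 2 mentions, 0 of 9 table rows and 0 planned analyses. It is a clerical inconsistency between sections of the form, which the sponsor can reconcile by stating whether the CGM is a token or a measure and making the sections agree. It does not alter the primary outcome, any secondary outcome, the sample size or the assignment. The income wording is equally minor, and describing the sample's economic circumstances from the baseline survey is ordinary reporting practice.

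The conclusion rests on three assumptions: that CGM means a continuous glucose monitor, that no confirmatory glucose comparison will be claimed, and that the consent text and attachments, which are not available here, do not make the CGM a study outcome. Uptake of the device and the low-income share are not stated, and neither figure is needed for this conclusion.

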## X. **Study Management:**

### A. **Oversight Plan:**

1. *Describe how the study will be implemented. List all parties, including collaborators and subcontractors, who will be “engaged” in the human subjects research project and their roles .*

[ The PI of the study is [name], an assistant professor in the department of international health. [name] will supervise all study staff including student research assistants and staff study coordinators. All study staff will complete the necessary human subjects research training modules. As this research is part of a K01 grant, [name] research mentor, [name] will also supervise and provide oversight for the study. ]

2. *What are the qualifications of study personnel implementing the project?*

[ [name] has a PhD in public health policy and has 7 years of experience conducting research. [name] is an Associate Professor in the division of General Internal Medicine at JHU with more than 10 years of experience conducting community interventions and implementing DPP in Baltimore. ]

3. *How will non-professional personnel (data collectors) involved with the data collection and analysis be trained in human subjects research ethical protections? (Use the JHSPH Ethics Field Training Guide available on the JHSPH IRB website. If the study is a clinical trial, consider using the JHSPH Good Clinical Practice (GCP) For Social and Behavioral Research Field Guide).*

[All study staff who interact with participants will do the Good Clinical Practice for Social and Behavioral Research training. ]

4. *If the JHSPH PI is responsible for data collection and will not personally be on-site throughout the data collection process, provide details about PI site visits, the supervision over consent and data collection, and the communication plan between the PI and study team.*

[ n/a ]

### B. **Protocol Compliance and Recordkeeping:**

*Describe how you plan to ensure that the study team follows the protocol and properly records and stores study data collection forms, IRB regulatory correspondence, and other study documentation. (For assistance, contact: [[contact]](mailto:[contact]) Please provide information about study oversight to ensure compliance with IRB approval and regulatory and institutional requirements. If the study team does not follow study procedure, what is your plan for reporting protocol non-compliance?*

[The study team will have a shared OneDrive folder in which all study documents and protocols will be saved. The study team will have weekly meetings, and every person brought on to the study team will have an orientation meeting with [name]. [name] will be responsible for all correspondence with the IRB and all other study documentation. ]

### C. **Safety Monitoring:**

1. Describe how participant safety will be monitored as the study progresses, by whom, and how often. Will there be a medical monitor on site? If yes, who will serve in that role and what is that person's specific charge?

[The participation in DPP does not pose any safety risks to participants and DPP do not exceed those of daily life. DPP is a proven preventive intervention and has not been associated with safety concerns in prior extensive research. However, [name] is a board certified general internist who will supervise all aspects of safety during this study. ]

2. If a Data Safety Monitoring Board (DSMB), or equivalent will be established, describe the following:

- a. The DSMB membership, affiliation and expertise.

[ n/a ]

- b. The charge or charter to the DSMB.

[ n/a ]

- c. Plans for providing DSMB reports to the IRB.

[ n/a ]

3. Describe plans for interim analysis and stopping rules, if any.

[ none ]

**D. Reporting Unanticipated Problems/Adverse Events (AEs) to the IRB (all studies must complete this section):**

NOTE: The IRB does not require PROMPT reporting of all AEs, only those that are **unanticipated, pose risk of harm to participants or others, and are related to the study.** Anticipated AEs may be reported with the Continuing Review/Progress Report.

Describe your plan for reporting to the JHSPH IRB, local IRBs, and (if applicable) to the sponsor. Include your plan for government-mandated reporting of child abuse or illegal activity.

[ While we do not anticipate any adverse events, should any arise (e.g. a person cutting themselves during class) we will report all adverse events to the IRB immediately. ]

